9.3.1.4 Patient-reported Outcomes Among Participants with PNH who Experienced an AESI

The only PRO used during this study will be a patient-reported fatigue assessment using the FACIT-Fatigue questionnaire.

9.3.2 Variables Specific to Participants with PNH Who Are Pregnant or Breastfeeding and Their Infants

For the participants with PNH who are pregnant, and their infants, additional pregnancy and infant outcomes will be evaluated as described below. Data will be collected from the participant by their hematologist physician.

9.3.2.1 Primary Safety Variables

9.3.2.1.1 Ectopic Pregnancy

Any reported ectopic pregnancy will be sub-classified in the respective pregnancy outcome, including induced termination, maternal death, or spontaneous pregnancy loss.

9.3.2.1.2 Spontaneous Abortion

A spontaneous abortion is defined as loss of a fetus due to natural causes at <20 weeks of gestation. Information on malformations will be requested if available.

9.3.2.1.3 Pregnancy Terminations (with or without Presence of Fetal Defects)

Pregnancy terminations are defined as any induced or voluntary fetal loss during pregnancy. Information on malformations will be requested if available. The reason for elective or therapeutic termination will be recorded.

9.3.2.1.4 Fetal Death or Stillbirth (with or without Fetal Defects)

Fetal death or stillbirth refers to fetuses born dead ≥ 20 weeks gestation or weighing ≥ 350 grams ([\[ACOG\] American College of Obstetricians and Gynecologists Obstetric Care Consensus No 2020](#)). Fetal death occurring ≥ 20 weeks but ≤ 28 weeks gestation is considered an early fetal loss. Fetal death occurring > 28 weeks is considered a late fetal loss ([\[ACOG\] American College of Obstetricians and Gynecologists Obstetric Care Consensus No 2020](#)). If gestational age is unknown, stillbirth refers to a fetus weighing > 350 g.

Data from gross or pathological examinations of the abortus or fetus will not be available; however, presence of abnormalities will be recorded.

9.3.2.1.5 Live Birth (with or without Congenital Anomaly)

A live birth refers to a complete expulsion or extraction from its mother of a surviving neonate. Information on malformations will be requested, if available.

9.3.2.1.6 Preterm Birth

According to the U.S Centers for Disease Control and Prevention (CDC), a live birth is classified as preterm prior to 37 weeks of gestation ([\[CDC\] 2024a](#)) as follows: early preterm (<34 weeks), late preterm (34–36 weeks), early term (37–38 weeks).

In the E.U, the classification of preterm birth aligns with definitions provided by the WHO and other medical guidelines as follows ([\[WHO\] World Health Organization 2023](#)): extremely preterm (<28 weeks gestation), very preterm (28–31 weeks gestation), moderate to late preterm (32–36 weeks gestation).

9.3.2.1.7 Size for Gestational Age

All live births will be classified as small, appropriate, or large for gestational age using the U.S. CDC definition of birth weight below the 10th percentile, between the 10th and

90th, and above the 90th percentile for age, respectively ([CDC] 2024b [WHO] World Health Organization 2006).

9.3.2.1.8 Low Birth Weight

An infant with low birth weight is classified as weighing under 2500 grams ([CDC] 1984, WHO 2011). Infants with very low birth weight are defined as infants who weigh < 1500 grams, while moderate low birth weight ranges between 1500 grams and 2499 grams.

9.3.2.1.9 Postnatal growth deficiency or failure to thrive (FTT):

Defined as weight below the 10th percentile for sex and chronological age using standard growth charts. Postnatal growth deficiency (or FTT) evaluation utilizes the sex-specific international growth reference standards from the World Health Organization (WHO) for children aged 0 to 24 months. Data on FTT will be collected during maternal hematologist follow-ups, and when feasible, FTT will be characterized retrospectively at 3, 6, 9, and 12 months of infant age.

9.3.2.1.10 Infant developmental deficiency:

Failure to achieve the developmental milestones for chronological age, as defined using CDC milestones across social/emotional, language/communication, cognitive, and movement/physical development categories, assessed separately for each. Similar to postnatal growth deficiency evaluation, developmental deficiency data will be collected during maternal hematologist follow-ups and characterized retrospectively at 3, 6, 9, and 12 months of infant age when feasible.

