7. RATIONALE AND BACKGROUND

Paroxysmal nocturnal hemoglobinuria (PNH) is a rare, acquired, chronic, life-threatening blood disorder associated with anemia due to hemolysis. It is most frequently caused by a somatic mutation in the phosphatidylinositol glycan class A (PIGA) gene of hematopoietic stem cells. The onset of PNH is often insidious. Although there have been reports of spontaneous remission, the course of the disease is generally chronically progressive.

The goal of PNH therapy is to control complement-mediated hemolysis and thus counteracting anemia. Hemolysis can result in a range of debilitating consequences, such as severe fatigue, chest pain, and transfusion dependence, all of which contribute to a reduced quality of life (QoL). If left untreated, PNH can cause severe and potentially fatal complications for patients. Thrombotic events are the main cause of severe complications and death in PNH. The disorder requires life-long treatment.

PNH appears to equally affect males and females, although there may be a slight female preponderance ([NORD 2024](#)). The disorder has no clear tendency toward a specific

race or ethnicity (Shah and Bhatt 2023). PNH has an annual incidence as high as 0.6 per 100,000 persons (Farooq 2020) and its prevalence is estimated to be 1–2 per 100,000 persons in the general population (Cançado et al. 2021). In the U.S., Europe, and Japan, the overall estimated number of patients with PNH is about 10,000 (Mandala et al. 2013; Ninomiya and Okura 2022). Although patients can develop PNH at any age, the typical age of presentation is between 30 and 40 years. Children can be diagnosed with PNH, though PNH diagnosis predominantly occurs during adolescence (Curran et al. 2012; Shah and Bhatt 2023). Pregnancy-related complications are also apparent in PNH, including worsening cytopenia, thrombosis, infections, bleeding, miscarriages, and increased maternal mortality; as well as adverse fetal outcomes of fetal death and premature delivery (Alashkar et al. 2020).

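### Infant growth and developmental deficiency are scored on chronological age, so preterm infants are more likely to be flagged because of early birth alone

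*Protocol*

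**What the plan says.** Both outcomes are primary variables for infants.

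- **Growth (Protocol 9.3.2.1.9).** FTT is "Defined as weight below the 10th percentile for sex and chronological age using standard growth charts". The reference is the "sex-specific international growth reference standards from the World Health Organization (WHO) for children aged 0 to 24 months".
- **Development (Protocol 9.3.2.1.10).** Deficiency is "Failure to achieve the developmental milestones for chronological age, as defined using CDC milestones", assessed separately in each developmental domain.
- **Timing.** Where feasible, "FTT will be characterized retrospectively at 3, 6, 9, and 12 months of infant age"; the same ages apply to development.
- **Prematurity.** Section 7 lists pregnancy complications of PNH, "as well as adverse fetal outcomes of fetal death and premature delivery". Section 9.3.2.1.6 makes preterm birth a primary variable of its own: "a live birth is classified as preterm prior to 37 weeks of gestation". Section 8.2 names gestational age among the infant outcomes.
- **Context.** Section 9.9.4 says that PNH may itself confound the pregnancy-related outcomes. Section 9.9.8 states that there is no comparator arm. Section 9.9.5 rules out obstetric and neonatal adjudication.
- **Related analyses.** Section 9.7.2 allows an optional sensitivity analysis that varies the timing of FTT and developmental deficiency. Corrected age and a term/preterm split for these two outcomes appear nowhere in the protocol.

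**The concern.** Time since birth is not the same as developmental age in an infant born early. A rule fixed on chronological age compares a preterm infant with term infants who have had several more weeks of development. The infant can then fall below the weight cut-off, or miss a milestone, while growing and developing normally for its gestational age.

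The protocol expects such infants in PNH whatever the drug does. An early delivery already counts under preterm birth, and under these definitions it also raises the chance of counting under growth deficiency and developmental deficiency. Without a control group carrying the same bias, a reader has only general-population expectations to set the result against, and the excess can look like a postnatal effect of crovalimab.

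This is a rule that the protocol states, not a detail left open for the SAP. An SAP that used corrected age as its main scale would depart from the protocol definition.

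**Working it through.** The protocol gives no figure of its own on this point; its one computed table (Table 2) concerns adverse events of special interest in 300 participants and does not enter here.

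**Inputs from the protocol:** 10th-percentile cut-off and chronological age (9.3.2.1.9); readings at 3, 6, 9 and 12 months (9.3.2.1.9 and 9.3.2.1.10); preterm means before 37 weeks (9.3.2.1.6); about 25 pregnant participants (9.5).

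**Assumptions, because the protocol gives none of these:** term is 40 weeks; one month is 4.345 weeks; preterm share f is 10% to 40%; weight shortfall d of a preterm infant on the chronological-age chart is 0.5 to 2 SD; for the counts, one assessed infant from each of 25 pregnancies.

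**Step 1, the age gap.** Corrected age = chronological age − (40 − gestational weeks)/4.345, in months. For birth at 32 weeks the gap is 8/4.345 = 1.84 months, so the 3-month reading is taken at 3 − 1.84 = 1.2 months corrected.

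| Born at (weeks) | At 3 months | At 6 months | At 12 months |
|---|---|---|---|
| 36 | 2.1 | 5.1 | 11.1 |
| 34 | 1.6 | 4.6 | 10.6 |
| 32 | 1.2 | 4.2 | 10.2 |
| 28 | 0.2 | 3.2 | 9.2 |

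The gap in weeks is constant, but it shrinks relative to age. At 32 weeks it is 1.84/3 = 61% of chronological age at the first reading and 1.84/12 = 15% at the last.

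**Step 2, chance that one preterm infant is flagged for weight.** P = Φ(−1.2816 + d), where −1.2816 is the normal quantile for 10%.

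- d = 0: 10%, by construction of the cut-off
- d = 0.5: 21.7%
- d = 1: 38.9%
- d = 2: 76.4%

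**Step 3, expected share in the cohort.** Share = (1 − f) × 0.10 + f × Φ(−1.2816 + d). Example: f = 0.4 and d = 2 give 0.6 × 0.10 + 0.4 × 0.764 = 36.6%. Expected counts in 25 infants are in brackets.

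| Preterm share f | d = 0 | d = 0.5 | d = 1 | d = 2 |
|---|---|---|---|---|
| 10% | 10% (2.5) | 11.2% (2.8) | 12.9% (3.2) | 16.6% (4.2) |
| 20% | 10% (2.5) | 12.3% (3.1) | 15.8% (3.9) | 23.3% (5.8) |
| 30% | 10% (2.5) | 13.5% (3.4) | 18.7% (4.7) | 29.9% (7.5) |
| 40% | 10% (2.5) | 14.7% (3.7) | 21.6% (5.4) | 36.6% (9.1) |

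The d = 0 column is what corrected age would give if preterm infants otherwise grow normally. Using one d for all readings is a simplification: larger values fit very early births and early readings better than the 12-month reading.

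**Step 4, against the precision available.** Clopper-Pearson 95% intervals for 25 infants are 2.5% to 31.2% for 3 flagged and 9.4% to 45.1% for 6 flagged. Both still contain 10%.

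No such calculation is possible for developmental deficiency, since the protocol gives no distribution of milestone attainment. The direction of the bias follows from Step 1.

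**The case against.** The strongest reply is that the study is descriptive, with no formal testing and no signal threshold for these outcomes. The preterm proportion will be reported beside them, Section 9.9.4 already warns of confounding by PNH and residual confounding, and Section 9.7.2 leaves further subgroup and sensitivity analyses to the SAP. At the mild end of the assumptions (10% preterm, 0.5 SD) the effect is 2.8 infants instead of 2.5.

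Much of this stands as a limit on how far the point goes. It does not remove the point, because the main definition is fixed on chronological age, and neither the general caveat nor the optional timing analysis changes it. The listed confounders are demographic, clinical, maternal and obstetric; the infant's gestational age at birth is not named as a stratifier.

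Four stronger readings are tempting and should not be made:

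- **That preterm infants as a group will be counted as deficient.** At a 1 SD shortfall, 61% of them (100% − 38.9%) are not flagged for weight.
- **That a false safety signal is likely.** The protocol sets no threshold for one, and 3 or even 6 flagged infants of 25 give an interval that contains 10%. The documents support only that the result can be misread.
- **That prematurity is formally counted two or three times.** The three variables are reported separately, and no composite adds them up.
- **That size for gestational age in Section 9.3.2.1.7 has the same fault.** That section uses "birth weight below the 10th percentile, between the 10th and" 90th percentiles and says in its heading and text that the classification is for gestational age. To hold that the cited charts are unsuitable would be to judge sources by their titles alone.

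**Conclusion.** The point holds as a matter of definition: on chronological age, preterm infants are more likely to be flagged for growth deficiency and developmental deficiency because of early birth alone. The distortion is greatest at 3 and 6 months, and no comparison within the study can remove it.

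The size is not known. Under the assumed ranges the expected share below the 10th percentile is about 11% to 37% instead of 10%, or 2.8 to 9.1 infants of 25 instead of 2.5. The bias is thus negligible at one end and dominates the estimate at the other. Those figures rest wholly on the assumed preterm share and SD shortfall, and they concern weight only.

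The change is worth making, because the protocol itself expects preterm births and the remedy loses no information.

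**What to change.** In Sections 9.3.2.1.9 and 9.3.2.1.10:

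1. For infants born before 37 weeks, score both outcomes on age corrected for gestational age at birth: chronological age minus the weeks short of 40.
2. Keep the chronological-age result as a sensitivity display.
3. Show both outcomes separately for term and preterm infants. Corrected age removes only the age shift; any true growth or developmental deficit that goes with prematurity will remain, and the split makes it visible.

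**Cost.** One derived age variable and one extra display. Gestational age at birth and the age at each milestone assessment must be recorded for every infant. Section 8.2 names gestational age as an infant outcome, but Table 1 does not list it explicitly at birth, and Section 9.9.5 promises exact timing for reporting only when feasible. Where milestones are entered only as a clinician's yes/no, they cannot be rescored by programming, and an added eCRF item in the silo registry may be needed.

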9.3.2.1.11 Congenital Malformations

Major malformations are those that have significant medical, social or cosmetic consequences, and typically require surgical intervention or are life-threatening (e.g., cleft lip, spina bifida). Minor malformations pose no significant health problem in the neonatal period and tend to have limited social or cosmetic consequences, rarely requiring surgical intervention (e.g., single palmar crease, clinodactyly). Both major and minor congenital malformations reported up to 1 year of age by the mother will be included in the analysis.

9.3.2.1.12 Serious and Severe Infections and Hospitalization of Infants

A serious infection will be defined as any infection in the infant that fulfills the definition of an SAE outlined in Section 9.3.1.3.1. Information on infant hospitalization will be requested if available.

9.3.2.1.13 Neonatal Death

A neonatal death is defined as a death occurring in a neonate prior to 28 days of life. In the event of a neonatal death, existence of fetal malformations will be requested.

9.3.2.1.14 Perinatal Death

Perinatal death is defined as the death of an infant between 28 days of life and 12 weeks of life. In the event of a perinatal death, existence of fetal malformations will be requested.

9.3.2.1.15 Infant Death

Infant death is defined as the death of an infant occurring between 12 and 52 weeks of life. In the event of an infant death, existence of fetal malformations will be requested.

9.3.2.1.16 Preeclampsia

A disorder of pregnancy associated with new-onset hypertension, which occurs most often after 20 weeks of gestation and frequently near term, and proteinuria ([\[ACOG\] American College of Obstetricians and Gynecologists 2020](#), [\[WHO\] World Health Organization 2011](#)). Or, in the absence of proteinuria, new-onset hypertension with the new onset of any of the following:

- Thrombocytopenia: Platelet count less than $100,000 \times 10^9/L$
- Renal insufficiency: Serum creatinine concentrations greater than 1.1 mg/dL or a doubling of the serum creatinine concentration in the absence of other renal disease
- Impaired liver function: Elevated blood concentrations of liver transaminases to twice normal concentration
- Pulmonary edema
- New-onset headache unresponsive to medication and not accounted for by alternative diagnoses or visual symptoms

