9.3.1.2.5 Serious Hemolysis

Serious hemolysis, onset and resolution date will be described. This event includes the following:

- New or worsening symptoms of PNH: fatigue, hemoglobinuria, abdominal pain, shortness of breath (dyspnea), anemia (hemoglobin < 10 g/dL), dysphagia, backache, headache, erectile dysfunction, chest discomfort, jaundice and other symptoms with detailed specification. Onset and resolution dates, and duration of symptoms will also be collected.
- Serious hemolysis, identified by serum lactate dehydrogenase (LDH) levels greater than the pretreatment level, along with any of the following: greater than 25% absolute decrease in PNH clone size (in the absence of dilution due to transfusion) in ≤ 1 week; a hemoglobin level of ≤ 5 g/dL or a decrease of > 4 g/dL in ≤ 1 week; angina; change in mental status; a 50% increase in serum creatinine level; or thrombosis.

Additionally, to contextualize hemolysis, the MAH will abstract the following:

- Possible alternative causes for the episode of hemolysis, including the presence of any complement-activating conditions.
- Proportion of PNH cells in granulocytes, monocytes, erythrocytes Type II/III, and reticulocytes.
- All medications used to treat or prevent the events of serious hemolysis.

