9.5 STUDY SIZE

Enrollment will depend on the approval timelines, uptake and treatment course in each country where the sites are open, as well as the total number of evaluable participants with PNH for AESIs (described in Section 9.3.1.2). However, based on patient projections in selected countries, the MAH expects 300 participants with PNH to be enrolled with up to 7 years of follow-up during the duration of the Crovalimab Silo registry (7 years).

[Table 2](#) provides probabilities (and associated 2-sided 95% CIs) to observe at least one event for AESIs with assumed prevalence ranging from 0.5%–20% in a population of 300 participants with PNH. For example, in the crovalimab trials, 6% of patients had a serious infection, 6.4% had an injection-related reaction, and 17.8% had a TICR, while no patients presented with a meningococcal infection or a serious hemolysis (Crovalimab E.U. Risk Management Plan [RMP] Version 1.0, 28 June 2024).

Table 2 Probability to Observe at least one Event for AESIs with Varying Prevalence

Assumed Prevalence ^a	Probability to Observe at least One AESI (95% CI)
0.5%	77.8% (10.2%–99.8%)
1.0%	95.1% (46.2%–100.0%)
1.5%	98.9% (74.3%–100.0%)
2.0%	99.8% (89.1%–100.0%)
5.0%	100.0% (100.0%–100.0%)
7.0%	100.0% (100.0%–100.0%)
10.0%	100.0% (100.0%–100.0%)
15.0%	100.0% (100.0%–100.0%)
20.0%	100.0% (100.0%–100.0%)

AESI = adverse event of special interest.

Note: 95% CIs are 2-sided and were calculated using Clopper-Pearson method (Clopper and Pearson 1934).

^a Assumed prevalence obtained during whole follow-up period.

In addition, the MAH aims to enroll approximately 25 participants with PNH who are pregnant in the Crovalimab Silo registry. Nevertheless, since the management of PNH during pregnancy has been challenging and pregnancy has been discouraged in participants with PNH, there are very few reported cases of pregnant participants with PNH treated with C5 inhibitors. For example, in a similar registry, there were only 94 pregnancies in fewer than 1,086 females treated with eculizumab from June 2006 to November 2014 (Kelly et al. 2015; Höchsmann et al. 2022).

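### Three primary outcome definitions need correcting: the preeclampsia platelet cut-off is 1,000-fold too high, serious hemolysis is ambiguous, and perinatal death is mislabelled

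*Protocol*

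**What the plan says.** All three variables are primary (Synopsis, Variables; Sections 9.3.1.2 and 9.3.2.1).

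- **Preeclampsia (9.3.2.1.16).** A case without proteinuria is "in the absence of proteinuria, new-onset hypertension with the new onset of any of the following". The first item is thrombocytopenia, given as "Platelet count less than $100,000 \times 10^9/L".
- **Serious hemolysis (9.3.1.2.5).** The section opens "Serious hemolysis, onset and resolution date will be described. This event includes the following" and gives two bullets. The first begins "New or worsening symptoms of PNH: fatigue, hemoglobinuria, abdominal pain, shortness of breath (dyspnea), anemia (hemoglobin < 10 g/dL), dysphagia, backache, headache, erectile dysfunction" and adds further symptoms; it sets no LDH condition and no seriousness condition. The second speaks of serious hemolysis identified by LDH above the pretreatment level together with one of several severity features. No word says whether the bullets are alternatives, jointly required, or a definition plus a data list. Table 1 footnote d restricts the event to participants who discontinue crovalimab; Section 9.3.1.2.5 does not.
- **Deaths after birth.** Neonatal death is before day 28 (9.3.2.1.13). "Perinatal death is defined as the death of an infant between 28 days of life and 12 weeks of life" (9.3.2.1.14). Infant death runs from week 12 to week 52 (9.3.2.1.15). Fetal death or stillbirth is a separate variable (9.3.2.1.4).

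**The concern.** The study has no comparator (Section 9.9.8), so misclassification cannot cancel between arms. A reported frequency can be read only against outside figures that carry the same name, so the name and the case rule must be right. Little downstream would correct them: Section 9.9.5 says obstetric and neonatal adjudication is not feasible and that hematologists collect these data, and the ENCePP checklist answers No to analytic control of outcome misclassification. The written definition is the main safeguard.

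**Working it through.** **Platelet cut-off.** The protocol derives no figure here, so the check is a unit conversion with 1 L = 10^6 microlitres.

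- As printed: 100,000 x 10^9/L = 10^14 per litre = 10^14 / 10^6 = 10^8 per microlitre.
- The same digits per microlitre: 100,000 per microlitre x 10^6 = 10^11 per litre = 100 x 10^9/L.
- Ratio: 10^14 / 10^11 = 1,000.
- Counts tried from 20 to 2,000 x 10^9/L all lie below the printed value. If one platelet occupies 5 to 12 fL (an assumption, not in the protocol), 10^14 of them fill 10^14 x 5 x 10^-15 = 0.5 L to 10^14 x 12 x 10^-15 = 1.2 L per litre of blood, so no real count reaches it.
- The protocol handles hemoglobin units consistently: 10 g/dL in 9.3.1.2.5 equals 10 x 10 = 100 g/L in 9.3.1.3.2. This points to an isolated slip.

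The effect depends on the reading. On the number alone, every new-onset hypertension satisfies this criterion. If the requirement of new onset is stressed, a condition that always holds can never newly arise, and the criterion drops out. It does not discriminate either way, and the direction of error is not fixed. With about 25 pregnant participants planned (Section 9.5), one misclassified case moves a proportion by 1/25 = 4 percentage points.

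**Serious hemolysis.** Setting the relevant sections side by side:

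| Place | What it requires |
|---|---|
| 9.3.1.2.5, bullet 1 | New or worsening PNH symptom, or hemoglobin below 10 g/dL; no LDH |
| 9.3.1.2.5, bullet 2 | LDH above pretreatment level plus a severity feature |
| 9.3.1.3.2, protocol-defined breakthrough hemolysis | Symptom or sign and LDH at least 2 x ULN after earlier reduction |
| 9.3.1.3.1, seriousness | Outcome or action criteria |
| Table 1, footnote d | Only participants who discontinue crovalimab |

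If bullet 1 alone qualifies, the primary serious event is easier to meet than the secondary breakthrough event and has no link to the seriousness criteria. Section 9.7.1 counts only the first event per participant and ends time at risk there. A symptom-only event would then add to the numerator, shorten the denominator and keep a later LDH-confirmed event out of the count.

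**Deaths.** In days, the windows are: neonatal, below 28; perinatal, 28 to 84 (12 x 7); infant, 84 to 364 (52 x 7). Every death called perinatal is therefore post-neonatal, and none near birth can be. A death in the first week is counted as neonatal, and a stillbirth under 9.3.2.1.4. The three windows leave no gap before day 364, although day 84 falls in two of them.

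**The case against.** Only the platelet figure is an arithmetic error, and even there the practical effect may be small. The item is headed thrombocytopenia and requires new onset, and outcomes are passively reported at visits by a nurse or hematologist. The protocol does not describe a program applying the cut-off, and platelets are not among the laboratory items it names, although that list is not exhaustive. A clinician is unlikely to call a normal count thrombocytopenia. This stands: a reader might infer that preeclampsia will be overcounted, and the protocol does not show that.

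On hemolysis, bullet 2 contains the word identified, bullet 1 ends with dates and durations to be collected, and a list of contextual data follows. The section can be read as one case definition with descriptive items around it. That reading is reasonable, but the opening words say the event includes both bullets, so it is not the only one. A reader might also set bullet 1 against the statement in Section 9.5 that in the crovalimab trials "no patients presented with a meningococcal infection or a serious hemolysis" and expect a large jump. The protocol supports no such figure. It gives no rates for the symptoms, the trials' definition of serious hemolysis is not shown, and bullet 1 concerns symptoms of PNH, not any headache or fatigue. Headache in Section 7 is listed as a common adverse event of crovalimab, which is a different thing.

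On deaths, all are captured under some heading, and a first-year total can be obtained by addition. That is correct, and it confines this part to labelling and comparability.

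**Conclusion.** The three parts differ in strength.

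- **Preeclampsia:** wrong as printed, by a factor of exactly 1,000. This rests on unit conversion alone. Inflation of the preeclampsia frequency is not shown.
- **Serious hemolysis:** ambiguous, so two programmers following the text could produce different counts and different person-time. Footnote d adds a conflict over who can have the event. The size of the effect cannot be derived from the protocol.
- **Perinatal and infant death:** mislabelled. A rate reported under either name would not mean what the name says, but no deaths are lost. This is the mildest part.

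No sample size or estimator changes. The corrections still belong in the protocol, since these are its own case definitions for primary variables and not details it defers to the SAP.

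**What to change.** 1. In 9.3.2.1.16, write the platelet cut-off as 100 x 10^9/L (100,000 per microlitre).
2. In 9.3.1.2.5, state that the LDH-plus-criterion bullet identifies a case and that the symptom bullet describes it. Reconcile this with Table 1 footnote d, so that one text says whether the event applies to all participants or only to those who discontinue.
3. Relabel day 28 to week 12 and weeks 12 to 52 as early and late post-neonatal death, and assign day 84 to one of them. Report all deaths from birth to 1 year as one figure, and a perinatal count built from fetal and early neonatal deaths, with its limits written out. The dates needed are those the current windows already require.

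The cost is wording in the protocol, eCRF guidance and programming specifications, with no new data collection. It is best done before the first data extraction, planned for Q1 2026.
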